Recent studies have indicated that a vaginal microbiome consisting of < 90% lactobacilli is associated with failure of IVF treatment (Data submitted for publication, ART PRED, Amsterdam) However, it remains unclear whether interventions designed to alter the microbiome are effective in changing the suboptimal microbiome diagnosed with these new tests, or how stable any induced change in microbiome might be. These questions are of particular importance to women planning IVF treatment, as an effective treatment may alter their prognosis in subsequent cycles. A number of approaches have been proposed, such as treatment with antibiotics and the use of probiotics. Vivag Plus (Bifodan, Hundested, marketed by Orkla, Ishøj) is a vaginal probiotic capsule containing lactobacilli species effective in relieving symptoms of bacterial vaginosis (Lægemiddelstyrelsen, 2017). It is hypothesized that this probiotic may also be effective in restoring lactobacilli dominance in the vaginal microbiome in women shown to have a profile associated with implantation failure. To test this hypothesis, the following research questions will be addressed:

Research questions

1. Compared with a placebo vaginal capsule, does the application of a lactobacilli loaded capsule for 10 days change a lactobacillus poor or by predictive vaginal test otherwise unfavorable vaginal microbiome, to a lactobacillus rich or by predictive vaginal test otherwise favorable microbiome in the same menstrual cycle as intervention?
2. Is the change in the microbiome still present one month after the intervention?

From this, our primary hypothesis is that compared with placebo, use of lactobacillus loaded vaginal capsule is associated with a significant increase in the proportion of women who demonstrate a shift from unfavorable to favorable vaginal microbiome.

III. Methods

Study design and population

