74 women diagnosed with suboptimal microbiome from either vaginal swabs or endometrial fluid sampling will be invited to participate in our double-blinded, randomized, controlled pilot study offering lactobacillus treatment to an intervention group of approximately 37 participants. The control group will receive placebo treatment with a placebo vaginal capsule. Information on medical and fertility history will be collected from patient journal after signed written consent from participants. Information on sexual life will be collected when participating in the study. Timing of last intercourse has shown to have an effect on the vaginal microbiome.

The Implantation Clinic

Since April 2017 Zealand University Hospital has been offering additional diagnostic work-up to women experiencing recurrent implantation failure (RIF= more than three consecutive transfers of high quality embryos). Patients demonstrating a suboptimal microbiome, will be invited to participate in the study. The results from the vaginal- and/or endometrial microbiome, are both part of the RIF-study and not part of diagnostic work-up. Information on microbiome from the RIF-study will be given to investigators in the present microbiome intervention study.

Additional subjects will be recruited from women attending the Fertility who have revealed a suboptimal vaginal microbiome following testing by their clinician and who meet the criteria for inclusion in the study.

The following flowchart gives an overview over the complete study.

Study flowchart

Figure 1: Overall study flow chart

[figure not shown]
[figure not shown]

Figure 2

Cycle with intervention (CD=cycle day)

Participant inclusion- and exclusion criteria

Patients diagnosed with suboptimal microbiome

- Age < 43 years
- Non-smoker
- Vaginal and/or endometrial microbiome suboptimal (<90% dominated lactobacilli)
- Attending Implantation Clinic, patient or control, and agreed to be contacted in case of other research study
- Patients attending fertility treatment in the Fertility Clinic in Køge and who have revealed a suboptimal microbiome following testing by their clinician, and who meet the criteria for inclusion in the study.

Exclusion criteria

- Age < 18 years
- Use of oral antibiotics between diagnose and inclusion
- Use of oral or vaginal probiotics with lactobacilli between diagnosis and inclusion

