Participants dropping out before the primary endpoint has been reached, will be replaced by additional recruits. However, it is anticipated that the drop-out will be <5%. Participants dropping out of the study at any point will be followed until the end of the study period for the individual participant. Participants failing to complete intervention with less than 50% of the study trial medicine, will be replaced.

The end of the study is defined as inclusion and test of the last participants one months after the first vaginal examination after intervention. See Figure 2. End of Trial for each participants will be the last visit to the clinic (third visit).

Study duration

Participant recruitment: September 3rd 2018 – December 31st 2019

Data Analysis: January 1st 2020 – February 1st 2020

Publication of results: March 1st 2020 – May 1st 2020

Biological material from participants

Microbiome material from the vagina

Size: One swab imbedded with bacteria from the top of the vagina.

Purpose: deep sequencing 16SRNA and qPCR from the bacteria to verify any suboptimal microbiome.

Analyzing: The vaginal swab will be send to be analysed abroad by ARTPred, in Holland. The samples will be stored and sent in a frozen state (-80 degrees or on dry ice respectively) in small batches of 10-30 samples. Storage of samples will take place in our fertility lab in Køge, where also sample collection will take place. Samples will be kept pseudo- anonymized and will be fully anonymized after the study is complete.

Analysis: ARTPred, The Netherlands will perform analyses. All samples will be sent pseudo-anonymized and in line with data protection legislation and the law of data protection.

Information from patient journals and research biobank

Information on medical and reproductive history will be collected from patient journal. All medical and fertility information from journals will be used within the study and in our Implantation Clinic. No personal information will be sent abroad. Samples sent will be identified with a participant number and date of sample collection. The participants will admit to use of journal medical- and reproductive history via consent forms. The Danish law on data protection will be followed.

A research biobank will be made to store the samples, between collection and analyses. Permission from the Data Protection Agency will be made simultaneously. All samples will be destroyed after analyses.

Data collection

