The patients in this study will already have undergone the initial work-up leading to the diagnosis suboptimal microbiome. At present no treatment has been shown to effectively treat or change the unfeasible microbiome present in the vagina and/or endometrium. Studies show that a *Lactobacillus* loaded environment in the female reproductive tract is important in order to have successful artificial reproductive treatment. The tests performed in this study are non-invasive and can be performed during fertility treatment, however our participants will be advised not to undergo fertility treatment during the study period, because of the hormonal effect from fertility treatment on the bacteria in the vagina. Clouding the results collected.

Recruiting participants and informed consent

Participants undergoing endometrial profiling in our Implantation Clinic and diagnosed with suboptimal vaginal and/or endometrial microbiome will be invited to participate, when they are informed about their work-up in the clinic. Investigation of the vaginal microbiome will be offered to patients undergoing fertility treatment in our Fertility Clinic. The vaginal swab will be performed at a routine visit in the clinic. This will provide the patients and the clinician with a prediction of the outcome of fertility treatment. Patients with a sub-optimal microbiome will hereafter be invited to participate in the present randomized controlled study. This can be done by phone or at a planned consultation. Before enrollment the participants will receive study information and "Participants rights when participating in a research project" by email or handed out during consultation. Hereafter, a consultation will be performed where the oral information will take place and a printed study information

and “Participants rights when participating in a research project” will be given. The oral information will be given according to guidelines in the field. See attached material. The oral information will be given by PhD-student [name] or health personal who have received the proper training and education. The consultation will take place in one of the clinics assigned rooms and behind closed doors. Before the participants consultation in the clinic they are informed about their right to an assessor. The informed consent will be collected after a suitable time of consideration.

Submission of results

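### Entry criteria bar only oral antibiotics, so a woman given a vaginal antibiotic after her qualifying test can enter a trial whose endpoint is a vaginal swab

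*Combined protocol and SAP*

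**What the plan says.** All references are to the combined protocol and SAP.

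- **Entry criteria** (III. Methods, exclusion criteria). Two neighbouring criteria cover earlier treatment: "Use of oral antibiotics between diagnose and inclusion" and "Use of oral or vaginal probiotics with lactobacilli between diagnosis and inclusion". Both run from diagnosis to inclusion. The probiotic criterion counts vaginal use; the antibiotic criterion does not.
- **Antibiotics during the trial** (III. Methods, last paragraph under Placebo). The rule for antibiotic use after entry also names the oral route only.
- **Background** (text before the research questions). On changing an unfavourable microbiome it says: "A number of approaches have been proposed, such as treatment with antibiotics and the use of probiotics".
- **Source of the qualifying result.** In the Implantation Clinic, "Since April 2017 Zealand University Hospital has been offering additional diagnostic work-up to women experiencing recurrent implantation failure", and "Information on microbiome from the RIF-study will be given to investigators in the present microbiome intervention study". In the Fertility Clinic a swab is taken at a routine visit, and "Patients with a sub-optimal microbiome will hereafter be invited to participate in the present randomized controlled study".
- **Recruitment period** (Study duration). "Participant recruitment: September 3rd 2018 – December 31st 2019".
- **Swabs** (Laboratory tests and examinations). Vaginal swabs are taken before treatment, after treatment and one month later. The text does not make eligibility depend on the first of these.
- **CRF content** (Data collection). The listed items do not name antibiotic or probiotic use. Medical history is taken from the patient's journal.

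**The concern.** The two criteria cover the same interval, and both concern products that the protocol treats as able to change the microbiome. They differ on route, and the route left out of the antibiotic criterion is the one applied at the sampled site. The protocol gives no reason for the difference.

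Three further gaps make the omission harder to detect afterwards. Nothing restricts use before the qualifying test, so a result obtained soon after a course of treatment still qualifies. Nothing limits the age of the qualifying result. And although a swab is taken before the first capsule, the plan does not use it to confirm that the woman still has the <90% profile on which she was selected.

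The stake is how well the randomised population matches the one the trial is meant to study. Women whose flora is changing for other reasons, or who no longer have the qualifying profile, contribute outcomes that say less about the capsule.

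**Working it through.** **1. Who passes the criteria as written**

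| Exposure | After diagnosis, before inclusion | Before diagnosis |
|---|---|---|
| Oral antibiotic | Excluded | Not restricted |
| Vaginal or other non-oral antibiotic | Not restricted | Not restricted |
| Oral lactobacillus probiotic | Excluded | Not restricted |
| Vaginal lactobacillus probiotic | Excluded | Not restricted |

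After diagnosis, the gap for the products these criteria address is antibiotics by a non-oral route. The right-hand column is open for every product.

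**2. How old a qualifying result could be**

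The protocol states no washout length or maximum age, so there is no figure to reproduce. Only a bound can be taken from the dates.

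Inputs: Implantation Clinic work-up offered from April 2017 (day not given); recruitment from 3 September 2018 to 31 December 2019. Months = days / 30.4375.

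- To the last recruitment day: from 1 April 2017, 1004 days = 33.0 months; from 30 April 2017, 975 days = 32.0 months.
- To the first recruitment day: from 1 April 2017, 520 days = 17.1 months; from 30 April 2017, 491 days = 16.1 months.

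This bound assumes that no qualifying sample predates the clinic's work-up. The protocol says the microbiome results belong to the RIF study and not to the work-up, and it does not date the start of that sampling. No minimum interval is stated either. Swabs are shipped abroad in batches of 10 to 30 with no turnaround given, and inclusion follows menstruation. If diagnosis means the swab date, weeks are therefore more plausible than days at the short end.

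**3. What it could do to the arm difference**

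The sample-size section plans for 64% against 36%, a difference of 64 − 36 = 28 points. The documents do not say how many women would be affected. As an assumption only, let a fraction f of both arms have the same one-month outcome probability r whichever capsule they receive. Then:

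- intervention arm: (1 − f) × 64 + f × r
- placebo arm: (1 − f) × 36 + f × r
- difference: (1 − f) × 28, whatever the value of r

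| f (assumed) | Difference, points |
|---|---|
| 0% | 28.0 |
| 5% | 28 × 0.95 = 26.6 |
| 10% | 28 × 0.90 = 25.2 |
| 20% | 28 × 0.80 = 22.4 |

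The model is severe, since it gives affected women no treatment effect at all. Because r cancels, it does not say whether the placebo rate rises or falls.

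**The case against.** The strongest defence is that these criteria are not a washout, and the protocol never calls them one. Women enter on an earlier result. A rule running from that result to inclusion protects it: exposure after the test makes the result unreliable, so the diagnosis date is the logical anchor and an interval that differs between women is expected. **This stands.**

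It also defeats the tempting remedy of a fixed look-back. Suppose a window of length w is applied before the qualifying swab and again before the pre-treatment swab, and the two swabs are L apart with L greater than w. Exposure in the first L − w of the interval is then covered by neither window. The current text excludes a woman with oral antibiotic or lactobacillus exposure in that stretch; the replacement would admit her.

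The same reasoning answers a reader who infers that the rule needlessly excludes women treated long ago but after an old diagnosis. Their qualifying result may no longer describe them, so excluding them is defensible.

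It can also be said that the sample-size section already allows for background change in both arms, that blinded randomisation balances earlier exposure in expectation, and that the flowcharts, not available here, may carry timing detail. The first two points limit the harm to noise and dilution. None of the three explains why vaginal use counts for probiotics and not for antibiotics. If the purpose is to protect the qualifying result, a vaginal antibiotic after the test is just the kind of exposure the rule should cover.

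**Conclusion.** The point holds as a gap in route and in confirmation of status. A woman given a vaginal antibiotic after her qualifying test is eligible as written; use before the test is unrestricted; the result has no maximum age; and eligibility is not tied to the pre-treatment swab. The likely effect is extra noise and a smaller arm difference. Its size cannot be derived from the documents, and the dilution table only illustrates an assumed fraction.

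A reader might infer three stronger things that the documents do not support:

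- **That the arms are systematically biased.** Allocation is randomised and double-blind, so earlier exposure is balanced in expectation. Chance imbalance remains possible with 37 per arm.
- **That intervals actually run from days to more than two years.** The 32 to 33 months is a bound from calendar dates, and the short end is undated. The extremes are also different problems: recent use before the test matters when the interval is short, an old result when it is long.
- **That recent vaginal probiotics slip through.** Vaginal lactobacillus products used after diagnosis do exclude; only use before diagnosis is uncovered.

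The conclusion rests on the eligibility text as written and on the assumption that the missing figures add no further rule.

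**What to change.** 1. Keep the diagnosis-to-inclusion window and extend the antibiotic criterion to any route. The oral-only wording on antibiotics during the trial, under Placebo, must be reconciled with it.
2. Add a CRF entry for product, route and stop date of antibiotics and probiotics, including use shortly before the qualifying swab.
3. Prespecify a sensitivity analysis of the primary endpoint restricted to women whose pre-treatment vaginal swab still shows <90% lactobacilli. That swab is already taken and precedes the first capsule, so the restriction cannot be influenced by treatment. Using it for analysis and not as an entry gate avoids holding up treatment while batched samples are sequenced abroad. The analysis should state that it also drops any woman who qualified on endometrial fluid alone and whose vaginal swab is not below 90%.

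**Cost:** a few women treated with vaginal antibiotics become ineligible, which matters slightly because the protocol names recruitment as its main risk. Beyond that, one CRF field and one extra analysis, which will be less precise than the primary one because it uses fewer women. No extra samples or visits are needed.

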- Pregnant at enrollment, since inclusion will happen after menstruation, pregnancy is not possible at the time of inclusion
- Allergy towards any of the content in the tablets

Laboratory tests and examinations

1. Gynecological examination: At all visits, the participants will undergo gynecological examination.
2. Vaginal microbiome: During the examination, a swab with vaginal secretion will be taken. In collaboration with Artpred (Amsterdam, The Netherlands) the vaginal microbiome will be identified by deep sequencing of the IS region of the 16SRNA gene using validated protocols. Samples will be collected using special swabs in fornix posterior in the vagina. After sampling the material will be inserted in a specialized buffer and saved for deep sequencing and qPCR. IS diagnostics will perform analyses on behalf of ARTPred.

Side effects, risks, and disadvantages

	Side effects	Risks	Disadvantage
Gynecological examination	No	No	Requires presence
Vaginal swab	No	No	Requires presence
Placebo supplements	No	No	Must be applied vaginally, increased vaginal discharge may occur
Vivag Plus supplement	No side effects registered	No	Must be applied vaginally, increased vaginal discharge may occur

Security measures include, sampling only collected by clinicians trained in the procedure. Participants will be informed about the procedure by phone before coming to the clinic.

Tests will be taken before treatment, after treatment, and one months after intervention or placebo at cycle day 21-25.

Randomization

Study participants will be randomized after inclusion and written consent forms have been signed. The study will be double-blinded. The manufacturer will distribute the packages unlabeled to Region Hovedstadens Apotek. The randomization and labeling will be orchestrated by the pharmacy using a validated computer based randomization program. The clinician and the participant will be blinded to the content of the packages. All packages will contain a total of 10 vaginal capsules and duration of treatment will be ten days. The duration of treatment is based on two previous studies, describing prolonged cure rate after treatment for ten days(Stray-pedersen *et al.*, 2008; Pendharkar *et al.*, 2015).

Intervention: Lactobacillus treatment

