There will be continuous monitoring and registration of compliance to the intervention, throughout the study. Participants will be asked to bring any excess study drugs at their first visit to the clinic, after the intervention. All excess study drugs will be registered in the CRF. Excess study drugs, handed back to the clinic will be destroyed. If participants forget to bring the excess study drug, registration of compliance will be done according to the participant’s memory. Rescue medicine is not applicable. Effect of treatment will be monitored throughout the primary and secondary end points. Throughout the study participants will be questioned about adverse events (AE=an unexpected medical event) and adverse reactions (AR= an unexpected/unintended response to a medical product) at every visit to the clinic. AE and AR will be registered in the trial clinical case reports and reported to the Sponsor within 24 hours.. All serious AE and serious AR (results in death, is life threatening, causes hospitalisation, or extension of hospital stay, results in disability or reduced incapacity) will be registered and investigator will report this to sponsor/principal investigator immediately and to the Danish Medicines Agency and the Ethical Committee, according to Lægemiddeloven §89. All serious AE will be assessed for causality before classified as a serious AR. Sponsor/principal investigator must also report suspected serious adverse reactions (SUSARs) immediately to The Danish Medicines Agency and ethics committee. All information regarding any SUSAR that is deadly or life threatening will be reported immediately and at the latest within 7 days after sponsor/principal investigator has been informed of the SUSAR. The sponsor/principal investigator reports all relevant information on sponsors and investigators follow up of the report within 8 days after the report. The sponsor must report all other SUSARs within 15 days of being informed of it. Every report should include comments on any implications and consequences for the trial.

The Danish Summary of Product Characteristics (Produktresume) is the reference document for evaluating whether a SAR is expected or suspected unexpected (SUSAR).

The ethics committee and the Danish Medicines Agency will receive yearly reports on security, and lists of serious AR. Reports will be send by the sponsor/principal investigator.

Statistical considerations, primary endpoint, study participants, and size

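### The adverse event definition is limited to unexpected events, so foreseeable events such as increased discharge may go unrecorded, and the wording is circular with the later expectedness step

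*Combined protocol and SAP*

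**What the plan says.** All wording on event recording is in the section *Registration of adverse events and/or reactions*. Participants are asked at each visit about adverse events ("AE=an unexpected medical event") and about "adverse reactions (AR= an unexpected/unintended response to a medical product) at every visit to the clinic". The recording rule follows: "AE and AR will be registered in the trial clinical case reports and reported to the Sponsor within 24 hours". Serious events and reactions are also to be registered and reported, and a serious event is assessed for causality before it is called a serious reaction. The Danish Summary of Product Characteristics "is the reference document for evaluating whether a SAR is expected or suspected unexpected (SUSAR".

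The table under *Side effects, risks, and disadvantages* has separate columns for side effects and disadvantages. For the active product the side-effects entry is "No side effects registered", and for placebo it is a plain no. For both, the disadvantage column reads "Must be applied vaginally, increased vaginal discharge may occur". The section on adverse reactions of Vivag Plus states that none are known.

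**The concern.** Whether an event was expected is normally asked after it has been recorded, and only to decide how a serious reaction is reported. Here the word *unexpected* is in the definition of an adverse event, so it acts as a filter on what is recorded at all. The protocol then asks about expectedness again for serious reactions, as though expected ones could still be present.

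What is at stake is the completeness of the safety record. If staff apply the definition literally, a foreseeable local complaint can be left out, and a report of few or no adverse events would partly reflect the definition. Discharge is not a trivial example here: the protocol's background text names it among the symptoms of a disrupted vaginal microbiome.

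**Working it through.** The plan gives no figure on this point, so the check sets its statements side by side.

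1. **Threshold for an adverse event.** The definition requires the event to be unexpected and offers no alternative. A foreseeable event does not meet it.

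2. **Threshold for an adverse reaction.** The definition joins *unexpected* and *unintended* with a slash. If the slash means *or*, a foreseeable but unintended response to the product qualifies. This route is open only when the event is attributed to the product.

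3. **What is registered.** The rule covers events and reactions as defined. No other route for non-serious events is described. The items named under *Data collection* (fertility treatment history, menstrual details, age, BMI, sexual history and test results) include no symptom item that would catch the remainder.

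4. **Increased discharge.** The table states for both products: "increased vaginal discharge may occur". It is therefore foreseeable and does not meet step 1. It can enter through step 2 if judged to be caused by the capsule, but the same table keeps it out of the side-effects column, which points staff away from that judgement. Discharge not attributed to the capsule has no clear route.

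5. **Expectedness step.** Serious reactions come from serious adverse events after a causality assessment. If every adverse event is unexpected by definition, a serious reaction reached this way cannot be expected, and one of the two categories is empty before the reference document is opened. The section also spells out SUSAR without *unexpected*. The word is thus present where it restricts recording and absent where it belongs.

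6. **Size.** The documents give no rate for increased discharge and no basis for the share that would be missed. With a rate p and a missed share m, the number missed per arm of 37 is 37 × p × m. Neither p nor m can be filled in from the documents.

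**The case against.** The strongest reply is that the text leaves more room than a literal reading of one definition suggests. Four parts of it have weight.

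- **The reaction definition includes unintended responses.** This is correct. A reader might infer that both events and reactions are confined to the unexpected, or that discharge will not be recorded. The documents do not support either: discharge attributed to the capsule can be registered as a reaction, and no section says it is to be left out. Women are questioned and examined at every visit. However, the questions concern events and reactions as defined, so they carry the same restriction.

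- **The expectedness step still works in practice.** This also stands. A reader might conclude that the SUSAR classification is impossible. It is a separate step against a named reference document, and since the protocol lists no known reactions, nearly every serious reaction would be classed as unexpected whatever the event definition said. The fault is circular wording. Nor do the documents name any anticipated serious reaction that would be lost.

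- **No between-arm safety test is planned.** The statistical section has none, the table entry on discharge is the same for both products, and the trial is double-blind. Nothing suggests that omissions would favour one arm. The counts reported for each arm could still be too low.

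- **Numbers attached to the problem do not measure it.** Assuming a discharge rate of 10–30% gives 3.7 to 11.1 women per arm of 37, but the rate has no source in the documents and the count assumes that none is registered as a reaction. Zero events in 37 women excludes only a rate above 1 − 0.05^(1/37) = 0.078, or 7.8% (one-sided 95%), but that limit comes from the sample size. It does not show that most of the safety information would be lost.

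The general commitment to ICH-GCP and Danish legislation in the quality assurance section does not rewrite the specific definition that staff are given.

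**Conclusion.** The adverse event definition is wrong as written. It makes expectedness a condition for recording, although the same section treats expectedness as a later question for serious reactions. The consequence is a risk of incomplete non-serious event counts in both arms, with increased vaginal discharge the event most exposed.

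This rests on two readings: that staff apply the definition literally, and that at least some foreseeable events are not judged to be unintended responses to the capsule. The size cannot be derived from the documents. Sample size, power, significance level and the primary endpoint are unaffected.

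**What to change.** In *Registration of adverse events and/or reactions*:

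- Define an adverse event as any untoward medical event in a participant, whether or not it is expected and whether or not it is related to the capsule.
- Define an adverse reaction as an untoward and unintended response judged related to the capsule.
- Use expectedness only at the SUSAR step, and include *unexpected* where SUSAR is spelled out.
- Reconcile this section with the table under *Side effects, risks, and disadvantages*, so that increased discharge is recorded when a participant reports it, whichever column lists it.

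A pre-listed discharge item on the CRF at the second and third visits, tabulated by arm, would be a useful option, but the correction does not depend on it.

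The cost is two rewritten definitions and a short reconciling sentence. Slightly more events will be recorded, and each will fall under the plan's 24-hour report to the sponsor.
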